1. **Study Purpose.** The primary purpose of this study is to experimentally evaluate two different comprehensive training models to train opioid treatment centers in an evidence-based behavioral treatment called contingency management (CM), which is the provision of motivational incentives for reaching specific treatment benchmarks. An exploratory goal of this study is to test whether theorized mechanisms of change – implementation climate and leadership engagement – mediate the effect of implementation condition on outcomes. Conduct of this study will address critical public health needs by (a) informing how CM, an evidence-based practice, should be implemented in OUD treatment centers, (b) improving the outcomes of OUD patients receiving treatment in the community, and (c) advancing knowledge about why and how implementation strategies work.
2. **Overview of Study Design.** A Type 3 Hybrid Trial will be conducted collecting data on both implementation and patient outcomes. We will use a 3-cohort staggered cluster RCT design. The unit of randomization will be opioid treatment centers. Centers will receive one of two comprehensive training conditions: the standard training provided by the New England Addiction Technology Transfer Center (ATTC training) or an enhanced condition that also provides leadership coaching and provider incentives (E-ATTC training). The primary research activities will be measuring the effectiveness of the training initiatives by gathering data from organizations, providers and patients.

Every 12-16 months, 10 OUD centers will be randomly selected to initiate study activities (10 centers X 3 cohorts = 30 centers). Prior to randomization, each center will complete a Baseline Organizational Assessment (described further in the Measures section) to collect organizational background data (e.g., years in operation, number of patients served annually, number of staff, medications prescribed, implementation readiness). Using these data, urn randomization procedures (balancing on number of patients served and percent of patients receiving methadone) will be used to randomize centers to either the ATTC or the E-ATTC condition. Centers in both conditions will complete a 5-month Preparation phase, a 9-month Implementation phase, and a 12-month Sustainment phase (26 months total). In both conditions, providers will record their delivery of CM in the electronic medical record and will audio record one CM session per month.

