Because this is an implementation trial, the goal is to help opioid treatment centers in both conditions to integrate CM into their routine clinical care. CM is a well-established, evidence-based behavioral intervention for the treatment of opioid use disorder; in fact, it has the strongest evidence base of any behavioral intervention. Its effectiveness as an

adjunct to medication has been documented in multiple systematic reviews and meta-analyses, it has large to very large effects, and in head to head comparisons, it has outperformed other behavioral interventions. Opioid treatment centers that participate in this study will receive training designed to help them universally offer CM to **all** newly admitted patients. In addition, front desk staff at the opioid treatment centers will be asked to give consent to contact forms to all newly admitted patients. Research staff will then make contact with interested patients and will obtain informed consent from up to 25 CM patients at each organization (25 patients * 30 organizations = 750 patients). Patients that provide informed consent will complete follow-up assessments at 3-months and 6-months post intake, to help assess whether the organizational training had positive effects on patient outcomes. Patients that do not wish to enroll in the study will still be eligible to receive CM sessions. In addition, those patients that do not wish to receive CM sessions can decline to receive CM or opt out of CM prize draws at any time. All patients will receive the standard of care at the opioid treatment center, which may or may not include CM.

3. **Study Participants.** Our primary unit of recruitment is OUD treatment centers. Within each center, we recruit a small number of providers to complete measures of organizational climate and functioning, to submit audio recordings of their sessions, to receive performance feedback on their sessions, and (for those randomized to E-ATTC) to receive performance incentives. We also consent 25 patients per center to complete study assessments so that we can track if our organizational intervention has a positive effect on patient outcomes.

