 - a. *Community-based OUD treatment centers (Centers).* A total of 30 centers will be included as part of the proposed study (see Attachments: Letters of Support). Centers were selected because they met the following inclusion criteria: a) prescribe FDA-approved medication to treat adult patients with OUDs; b) enroll 5+ new patients per month; and c) have at least 2 staff who provide psychosocial support to OUD patients.
 - b. *Community-based OUD treatment center providers (CM Providers).* Drs. [name] and [name] will work with each participating opioid treatment center to identify front-line treatment providers and leaders eligible for the study.

Eligible providers will be any front-line treatment provider who has: a) been involved in providing psychosocial support to OUD patients on pharmacotherapy, b) an active caseload, c) been employed by the opioid treatment center at least 3 months, and d) willingness to commit to 14 months of CM training and support. All eligible treatment providers at the centers will be invited to receive the CM didactic training. However, centers will nominate 2-5 providers to serve as “CM champions”: the “CM champions” will complete periodic measures of organizational climate (described further in Measures), submit monthly audio recordings of their sessions, receive performance feedback on their audio recordings, and (for those randomized to E-ATTC) will receive performance incentives. In our experience with centers in a recent pilot study, none had more than 5 staff, so for the vast majority of sites, we expect to be able to invite all staff to participate. Thus, between 60-150 CM Providers (30 centers x 2-5 CM Providers per center) will complete measures across the three cohorts (20-50 CM Staff per cohort).

Eligible leaders will be: a) responsible for supervising frontline CM Staff, b) have been employed by the opioid treatment center at least 6 months, and c) be willing to commit to 14 months of external leadership coaching. Thus, in addition to the 60-150 CM providers, another 60 leadership staff (30 centers x 2 leaders per center) will provide data.

There is an annual staff turnover rate of approximately 30% among substance use disorder treatment providers and 20% among leadership staff. Although we invite 2-5 front-line providers from each center to participate in the study, we allow each center to send as many providers to the CM training as desired. Given the likelihood that about

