- c. *Patients.* Front-desk receptionist staff in each of the participating centers will give new patients that present to treatment a consent to contact form. Patients that are interested in participating and sign a consent to contact form will then receive a call from the local research team to set up a time to complete the consent and baseline assessment process. It is expected that opioid treatment centers will only refer eligible patients. But as a safeguard, at the start of the call, research staff will confirm eligibility for the study using the brief 3-item **Patient Screener**. To reduce the amount of PHI stored at each treatment center, consent forms will be administered to eligible patients electronically and will use electronic signatures. Patients will have the option of completing the consent process via phone at a location of their choosing if they have access to the internet and can review the consent form during the phone call, via phone in a private room at the opioid treatment center with a study research tablet that contains the consent form, or in person with research staff at the opioid treatment center. Patients will receive a copy of the form electronically or via mail: their preference will be assessed in the consent form. Estimates from the 30 participating centers indicate the average patient flow is 17 new patients per month or 102 patients per 6-month period. Our recruitment targets conservatively estimate that 25% of new patients will be enrolled, for a total of 750 patients (30 clinics x 25 clients per center). If necessary to reach our target sample size (750), we will oversample from larger centers; if so, we will monitor patient enrollment and ensure a balanced number of patients are assigned to the two implementation conditions (ATT vs. E-ATT).

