Incentive amounts are designed to enable staff to, on average, earn bonuses that during a 12-month period would comprise about 6% of their mean annual base salary of US \$45,000. Prior P4P research^{18,19} has suggested that bonuses between 4 and 7% are large enough to significantly improve staff performance, yet modest enough to be practical for community treatment centers to implement. Provision of incentives will follow the exact same schedule of provision of performance feedback reports described in 7a. Sessions must be submitted by the last day of the month and must be from that calendar month. Within 2-4 weeks following submission of recordings, providers in the E-ATTC condition will receive email notifications from research staff containing their performance feedback reports, as well as confirmation of their achievement of CM Exposure and CM Competence for the prior month. CM staff enrolled in the E-ATTC condition will receive payments via cash, check, or Clincard.

8. Data Collection Procedures.

- a. *Organizational background form.* Prior to randomization, leaders at each center will collaboratively complete an Organizational Background Form via Qualtrics. Data collected will include, but not be limited to: number of patients, proportion of patients on different OUD medications, number of staff, average staff tenure, and years in operation.
- b. *Staff surveys.* After randomization, CM staff and leadership staff will complete two online Qualtrics surveys: one at the start of the Preparation phase and one at the midpoint of the Implementation phase. The first survey (30-45 minutes) will contain the following measures: Provider Demographics, Organizational Readiness for Change, Attitudes towards CM, and putative mediators (i.e., Implementation Climate, Leadership Engagement). The second survey (15-30 minutes) will only evaluate the putative mediators. Participating staff will receive \$25 for the first and \$20 for the second survey. We attained 82% or higher completion rates on comparable staff follow-up surveys in the New England ATTC pilot.

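### Two of the three primary outcomes count CM sessions, but the plan states no center-level baseline for CM delivery before randomization

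*Combined protocol and SAP*

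**What the plan says.** References are to the combined protocol and SAP, part B (Detailed Study Methodology), unless stated otherwise.

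- **Center eligibility (3a).** There are three conditions for inclusion: "a) prescribe FDA-approved medication to treat adult patients with OUDs; b) enroll 5+ new patients per month; and c) have at least 2 staff" giving psychosocial support. None concerns existing CM, and no center-level exclusion is stated.
- **Outcomes (9a).** CM Exposure counts sessions per enrolled patient in the 9-month Implementation phase. CM Sustainment counts sessions per patient in the 12-month Sustainment phase, among newly admitted patients.
- **Timing of the counts (8d).** Session data are extracted twice, at the end of each of those phases. There is no extraction before randomization.
- **Pre-randomization form.** The Overview of Study Design (2) gives as examples "years in operation, number of patients served annually, number of staff, medications prescribed, implementation readiness". Section 8a names "number of patients, proportion of patients on different OUD medications, number of staff, average staff tenure, and years in operation", and says the data are not limited to these. Section 9d lists similar items.
- **Randomization (2).** The urn balances on two factors, patient volume and the share of patients on methadone.
- **Models (10b).** The organization-level covariates, again given as examples, are years operating, patient numbers, medications and readiness. Each covariate is first tested as a moderator of condition and becomes a control variable only if no moderation is found.
- **Existing CM.** The Lay Summary (section 1) describes uptake of CM in treatment centers as low. The Overview (2) says "All patients will receive the standard of care at the opioid treatment center, which may or may not include CM". No number of participating centers already using CM is given.

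**The concern.** Prior delivery of the same practice is the natural baseline for a count of how much of it is delivered. Only 30 units are randomized, so a few centers with an established CM program could fall unevenly between the arms and would add to between-center variance.

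Interpretation is also at stake. In the Sustainment phase no training or coaching is given in either arm (6c). A center continuing a program it ran before the trial could then look the same as one that took CM up because of the trial. The chance to record a clean baseline prospectively is short, because all centers in both arms are trained in CM during the Preparation phase (6a).

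**Working it through.** **The plan's own figures.** The design has "10 OUD centers will be randomly selected to initiate study activities (10 centers X 3 cohorts = 30 centers"), and 10 × 3 = 30. Enrollment is "for a total of 750 patients (30 clinics x 25 clients per center"), and 30 × 25 = 750. Both reproduce. The plan states no power, alpha, effect size, SD or intraclass correlation, so there is no power figure to check.

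**Assumptions, none of them in the documents.** k = 2 or 3 of 30 centers already deliver CM; allocation is 15:15; these centers deliver D extra sessions per patient, with D = 1, 2, 3 or 6; between-center SD is 2 sessions and within-center SD is 3.

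**1. Chance that all k centers fall in one arm.** P = 2 × C(15,k) / C(30,k).
- k = 2: 2 × 105 / 435 = 0.483.
- k = 3: 2 × 455 / 4060 = 0.224.

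If each cohort of 10 is split 5:5, the figures are similar. For k = 2 they are 0.44 (same cohort) to 0.50 (different cohorts). For k = 3 they are 0.17 (all in one cohort) to 0.25 (one in each).

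**2. Shift in the arm difference under a 3–0 split.** Shift = 3 × D / 15.
- D = 1: 0.2 sessions.
- D = 2: 0.4.
- D = 3: 0.6.
- D = 6: 1.2.

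**3. Inflation of the standard error of the condition effect, k = 3.** The variance of a center mean without the CM-use difference is 2² + 3²/25 = 4 + 0.36 = 4.36. Unmodelled prior use adds 0.1 × 0.9 × D² = 0.09 × D². The ratio of standard errors is √[(4.36 + 0.09 D²) / 4.36].

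| D | Added variance | Ratio | Inflation |
|---|---|---|---|
| 1 | 0.09 | √(4.45/4.36) = 1.010 | about 1% |
| 2 | 0.36 | √(4.72/4.36) = 1.040 | about 4% |
| 3 | 0.81 | √(5.17/4.36) = 1.089 | about 9% |
| 6 | 3.24 | √(7.60/4.36) = 1.320 | about 32% |

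D = 6 is three of the assumed between-center SDs, so the last row is an extreme case. The ratios do not deduct the cost of the covariate itself (one degree of freedom, and some correlation with arm in a lopsided split). They are upper bounds on the gain, and at D = 1 little or no net gain in precision should be expected.

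**4. If no center uses CM at entry,** the item is constant, there is no imbalance, and the inflation is zero.

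**The case against.** Five points can be made against the concern, and most of them stand in part.

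- **The lists are open.** Sections 2, 8a, 9d and 10b all present their lists as illustrative, and the forms themselves are not in the documents. A reader might infer that the form lacks a CM item and that nothing could be adjusted for. The documents show only that the item is not named. Even so, an item that is neither named nor pre-specified does not protect the primary analysis.
- **The standard-of-care sentence is ambiguous.** A reader might take it as an admission that enrolled centers already run CM. It directly follows sentences on patients who do not enroll, or who decline CM, so it may describe care during the trial. The point does not need it: sections 3a, 8d and 10b carry it.
- **Legacy sessions are not counted automatically.** A reader might infer that sessions from an existing program would all enter the outcome. Under 8d and 9a a session counts only if it was documented on the study's self-report form and then extracted. Centers in both arms also set a compliance benchmark for the trial (6a), and staff must pass practice sessions before being assigned patients (7a). Prior experience could still raise the documented count, but by how much is unknown.
- **Few centers may be affected.** Low uptake makes zero a plausible number, and any head start may fade once all centers are trained. This stands. Few is not none, however, and with 2 or 3 such centers lopsided splits are common.
- **There is no validity error.** A reader might infer that the primary comparison is biased. Randomization keeps it unbiased in expectation, and unexplained between-center variation enters the standard error through the center level of the model. This stands in full.

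**Conclusion.** The gap is real but modest. Centers already delivering CM are not excluded, no session count precedes randomization, and current CM delivery is not a named baseline item, urn factor or covariate. CM Exposure and CM Sustainment therefore have no stated center-level baseline. What may be lost is precision, protection against chance imbalance, and the ability to separate new adoption from continuation of an existing program.

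The documents do not allow the loss to be sized. Under the assumptions above it runs from nothing (no center using CM) through 1% to 9% on the standard error (1 to 3 extra sessions) to 32% in an extreme case. They do not support the stronger conclusions that the comparison is biased, that enrolled centers are known to run CM, or that no adjustment would be possible. This is a cheap improvement of modest priority.

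**What to change.** - **Form.** Add to the Organizational Background Form, completed before randomization, whether the center currently delivers CM and the approximate share of new patients who received it in the past 6 months.
- **Model.** Pre-specify this as a single center-level main-effect covariate for CM Exposure and CM Sustainment, stating in advance which coding enters the model. Drop it if all centers report none.
- **Exemption.** Exempt it from the moderation-first step in 10b. If all CM-using centers fall in one arm, the condition-by-use interaction cannot be estimated.
- **Sensitivity analysis.** Repeat both analyses without the centers already delivering CM. The exclusion rests on a characteristic recorded before allocation, so it does not condition on anything the trial caused.

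The cost is one or two items on a form every center already completes, and one center-level degree of freedom, spent only if some centers report CM. If none do, the trial can report a zero baseline. For any cohort already randomized, the items can only be asked in retrospect and should be labelled so.

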one of three trained CM staff will turnover during the project's first two phases, each center will be required to identify one or more replacement CM staff. Thus, if one of the initially trained CM staff withdraws from the study for any reason during the Preparation or Implementation phase, a replacement CM staff will be immediately trained.

- c. *Community-based OUD treatment center patients (Patients).* Each center will agree to deliver CM to all patients newly admitted over a 6-month period. In addition, each center will be asked to enroll approximately one eligible CM patient per week to complete research assessment measures. Eligible patients will be: a) adult patients, b) newly admitted to the opioid treatment center within the past 30 days, and c) prescribed any FDA-approved OUD medication. To optimize ecological validity, exclusion criteria will be minimal and will only include issues that could interfere with the ability to complete a brief intake interview including acute intoxication, acute psychosis, acute mania, or cognitive impairment (prohibiting comprehension of the consent process), as reported by opioid treatment center staff or observed by research staff. We focus on newly admitted patients as opposed to those established in treatment because the need is highest among these patients: drop-out rates and missed doses are higher during the first 6 months of treatment (i.e., the "induction phase") than any subsequent period.

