- c. *Patient assessments.* Patients will complete assessments at baseline and at 3 and 6 months post-intake. Brief baseline assessments will be conducted by research staff either in person at the participating centers or via phone. Multiple strategies will be used to prevent attrition. At baseline, multiple sources of contact information will be recorded for patients. Contact information will be updated by periodic phone calls. In addition, patients will provide detailed contact information of two friends or family members ("locators") who can be contacted if research staff is unable to reach them. Reminders will be made via phone, text, and email: the reminders will not contain any details about the study and will simply note a reminder about an upcoming appointment. Patients who cannot be reached over the phone for follow-up will be identified as needing follow-up from the designated outreach team, who will attempt in-person contact in at the patient's home or OUD center. Patients will receive a slightly escalating schedule of compensation in the form of a Clincard, a reloadable Mastercard card for completing the baseline (\$20), 3-month (\$20), and 6-month follow-up (\$25) assessments. Our analysis plan assumes 80% completion of patient follow-up assessments.

- d. *Electronic medical record (EMR)*. All 30 sites have agreed to document CM session delivery in their medical records (using the Post-Session Self-Report Form) and to extract patient data into an online Qualtrics template created for this project (using the Medical Record Data Extraction Form). Providers will enter session data into the Post-Session Self-Report Form in the medical record. Data will be extracted from the medical record from staff at the participating opioid treatment centers at two timepoints: a) end of 9-month Implementation phase and b) end of 12-month Sustainment phase.

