 - iii. **CM Sustainment**. This is a patient-level measure of the number of CM sessions delivered per patient during the 12-month Sustainment phase. Using the same protocol as for CM Exposure, data will be extracted at the end of the Sustainment phase from 25 randomly selected patients meeting eligibility criteria (i.e., newly admitted to OUD pharmacotherapy during the Sustainment phase; 25 patients * 30 sites = 750 patients). A continuous measure of the number of sessions received, as counted by the number of Medical Record Data Extraction forms completed, will be created for each patient.

b. *Patient outcomes.* Our **Secondary Aim** tests the effectiveness of the two implementation conditions (ATTC vs. E-ATTC) on two patient outcomes: Opioid Abstinence and Opioid-Related Problems.

- i. **Opioid Abstinence.** Patient abstinence from opioids will be assessed via 3- and 6-month post-baseline interviews, during which patients will self-report days of abstinence using the Timeline Followback (TLFB).²⁰ Abstinence will be corroborated via dip urine screens from Redwood Toxicology testing for: heroin/opiates, oxycontin, benzodiazepines, cocaine, methamphetamines, and THC. In addition, at the request of participating centers, single-panel screens will test for fentanyl, a highly lethal opioid not detected in multi-panel screens. A urine screen negative for all opioids (heroin/opiates, oxycontin, fentanyl) will be required for coding of 90 days abstinence. Other drug use detected via the TLFB or urine will be examined as covariates in the analysis.
- ii. **Opioid-Related Problems.** Opioid-related problems will be assessed via patient self-report at 3- and 6-months post-baseline using the Substance Problem Index,²¹ which is a count of DSM symptoms experienced by the patient (range from 0 to 11). Both Drs. [name] and [name] have successfully used this index²²⁻²⁴ in prior studies. The index will be tailored to focus specifically on problems due to opioids.

c. *Putative mediators.* Our **Exploratory Aim** tests putative mediators of implementation outcomes: implementation climate and leadership engagement. Organization-level scoring is described in **Analytic Plan**. The putative mediator scales are measured at the start of the Preparation phase and the midpoint of the Implementation phase.

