- b. For the **Primary and Secondary Aims**, we test a series of multilevel models in which patients (Level 1) are embed within staff (Level 2) and within centers (Level 3). Consistent with Raudenbush and Bryk's multilevel modeling approach,³² the proportion of variance to-be-explained at each level will be examined as an initial step. Next, following a decomposed-first strategy that advocates for starting with moderation-focused hypotheses to avoid biases associated with conflated effects,³³ we conduct multilevel regressions testing the extent to which our covariates significantly moderate the hypothesized relationship between condition and outcome. We test covariates at three levels: organizational (e.g., years of operation, number of patients, medications prescribed, implementation readiness), staff (e.g., tenure, education, CM attitudes), and patient (e.g., age, race, biological sex, problem severity). If moderation is not found, covariates will be controlled for as predictors. Condition assignment (ATTC vs. E-ATTC) will be the primary independent measure of interest for analyses. In addition to reporting statistical significance, we will report the effect size (ES) using Cohen's d .³⁴
- c. For the **Exploratory Aim**, we again test a series of 3-level models. For each mediator, the average correlation within group (r_{wg}) will be computed to determine whether aggregation of staff level responses to the organizational-level is warranted. Values of r_{wg} range from -1.00 to 1.00, with values $\geq .60$ representing acceptable agreement.³⁵ Centers with r_{wg} values $< .60$ will be excluded from analysis. Exploratory analyses will apply a Baron and Kenny³⁶ style mediation approach,

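### Baseline problem severity, used as moderator or covariate, can be measured after CM has begun, and follow-up is timed from intake in two places but from baseline in a third

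*Combined protocol and SAP*

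**What the plan says.** All references are to the numbered items of the Detailed Study Methodology in the combined protocol and SAP.

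- **Entry.** Item 3.c makes adults eligible if "newly admitted to the opioid treatment center within the past 30 days".
- **Who gets CM.** The same item says "Each center will agree to deliver CM to all patients newly admitted over a 6-month period". Item 2 adds "Patients that do not wish to enroll in the study will still be eligible to receive CM sessions", so CM does not wait for study consent.
- **Order of events.** Item 2 randomizes centers after an organizational assessment and before the phases in which patients are treated and enrolled. Item 4.c describes the route into the study: a form at the front desk, a research call, a screener, consent, then baseline. No item requires baseline to come before the first CM session.
- **Use of severity.** Item 9.d measures problem severity at baseline only. Item 10.b includes it among the patient-level covariates, "patient (e.g., age, race, biological sex, problem severity", tests these as moderators, and otherwise keeps them in the model as predictors.
- **Follow-up anchor.** Item 2 has consenting patients "complete follow-up assessments at 3-months and 6-months post intake". Item 8.c says "Patients will complete assessments at baseline and at 3 and 6 months post-intake". Item 9.b says "Patient abstinence from opioids will be assessed via 3- and 6-month post-baseline interviews" and "Opioid-related problems will be assessed via patient self-report at 3- and 6-months post-baseline". Intake is not defined.

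**The concern.** A baseline covariate is safe to adjust for when treatment cannot have touched it. Here allocation is at center level and already made, and the two conditions are designed to produce different amounts and quality of CM. If a patient has had CM before the baseline interview, severity at that interview can already reflect the condition. Adjusting for it then credits part of the condition effect to the covariate. Testing it as a moderator has the same fault, because the subgroup variable is no longer pre-exposure. Item 10.b offers only these two uses.

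The outcomes exposed are those of enrolled patients: CM Exposure (primary), and abstinence and opioid-related problems (secondary).

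The anchor is a separate matter. Two readers following different items could schedule the same patient's 3-month visit up to 30 days apart.

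**Working it through.** **Plan's own figures.** The plan gives no figure for the admission-to-baseline lag. Its patient target reproduces: 30 centers × 25 = 750 (from flow: 17 × 6 = 102 new patients per center, 25% = 25.5, × 30 = 765). The point does not depend on that target.

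**Inputs from the plan.** Lag L from 0 to 30 days (item 3.c). Prize draws at least weekly, for up to 12 weeks, which is 84 days (item 5). Target of 10 sessions out of a maximum of 24 (item 9.a.i). A 90-day abstinence period, implied by the coding rule in item 9.b.i; the length of the Timeline Followback window is not stated.

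**Assumptions, not in the plan.** CM starts at admission. The difference between conditions in problems builds evenly over 84 days. Severity is on the same scale as the outcome and reflects status at the interview. The severity coefficient b is 0.3 to 0.7.

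**Step 1: sessions before baseline.** At L = 30 there are 4 whole weeks, so 4 weekly sessions: 4/12 = 33% of a 12-week course and 4/10 = 40% of the target. If sessions are twice weekly, which would fit the maximum of 24, it is 8.

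**Step 2: share of the effect removed by adjustment.** Let D be the condition effect on problems after 84 days. At lag L, baseline severity already differs by (L/84) × D. Adjustment subtracts b × (L/84) × D, so the share removed is b × L/84.

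| Lag if common to all patients | L/84 | b = 0.3 | b = 0.7 |
|---|---|---|---|
| 7 days | 0.083 | 2.5% | 5.8% |
| 15 days | 0.179 | 5.4% | 12.5% |
| 30 days | 0.357 | 10.7% | 25.0% |

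The formula is linear in L, so with varying lags the mean lag governs. The last row needs every patient to enrol on the last eligible day.

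**Step 3: which outcomes.** CM Competence is a staff-level score (item 9.a.ii). CM Sustainment uses other patients, admitted in the Sustainment phase (item 9.a.iii). Neither is reached by this route.

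**Step 4: the anchor.**

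- If intake means admission, the 3-month visit falls 90 − L days after baseline, and L of the 90 days precede baseline. At L = 30 this is 60 days and 30/90 = 33%; at 14 days, 14/90 = 16%; at 7 days, 7/90 = 8%. The 6-month window covers days 91 to 180 after admission, so it holds no pre-baseline days at any allowed lag.
- If intake means the study baseline, neither window holds pre-baseline days, and the 3-month visit falls 90 to 120 days after admission.

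**The case against.** The strongest reply is that much of this may be small or merely verbal.

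- **The lag may be short.** Item 4.c has front-desk staff hand out the contact form when patients present, so 30 days is a ceiling. This stands, and is why the 7-day row belongs beside the 30-day row.
- **The recall period may protect the covariate.** No instrument or recall period is given for baseline severity. If recall lies mostly before admission, contamination is small. This stands as a possibility, and stating the period would settle it.
- **The direction is not certain.** It also depends on unmeasured causes shared by severity and outcome. This stands; toward zero is the likelier direction, not a guaranteed one.
- **Intake may mean the research interview.** Item 3.c speaks of an intake interview when listing exclusions, apparently the study's own, and item 9.b, which defines the outcomes, uses baseline for both. This stands against treating the 3-month overlap as established, but the term is still undefined.

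A reader might also infer that counting sessions delivered before enrolment is an error in CM Exposure. The documents do not support that. Item 9.a.i defines the outcome as delivery over the Implementation phase, and CM given before a patient's consent is still delivery under the center's assigned condition.

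A reader might further infer that the lag differs by arm, since center staff hand out the forms and E-ATTC pays for sessions. No item describes such a difference: the forms go to all new patients, research staff do the consenting, and the bonuses go to CM providers.

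What the reply does not answer is that CM may precede baseline and item 10.b uses severity regardless.

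**Conclusion.** The concern holds for baseline severity. Nothing keeps that measurement ahead of condition-dependent CM, and the planned models all use it. The likely consequence is some attenuation of the condition effect on the outcomes of enrolled patients. The percentages are illustrations for the problems outcome under the assumptions listed and do not transfer directly to CM Exposure or abstinence. On those assumptions the loss is a few percent at short lags; a quarter is an extreme, not an expectation. A reader might take the bias to reach the whole primary aim, but CM Competence and CM Sustainment are not affected through this route.

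The anchor mismatch is real as text. Its consequence is conditional: it needs intake to mean admission, and then it touches only the 3-month window. It would be wrong to conclude that both follow-up windows include pre-baseline time.

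This should be corrected, chiefly because recall wording and dates are hard to recover once patients have been interviewed. It does not invalidate the design.

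**What to change.** 1. Ask the baseline problem-severity items about a fixed period ending on the admission date, and state that period in item 9.d.
2. Use the baseline anchor of item 9.b in items 2, 8.c and 9.b, and define intake.
3. Record the dates of admission, first CM session and baseline. Item 8.d does not say that session dates are extracted, so this may need an added field.
4. Report the admission-to-baseline lag by arm, and use it only in a sensitivity analysis. It should stay out of the main model, because it arises after allocation and could itself be affected by condition. The sensitivity analysis also addresses the 90-to-120-day spread from admission that remains under a baseline anchor.
5. Leave CM Exposure as the count over the Implementation phase.

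The cost is reworded items, three dates and one sensitivity analysis, with no added visits or patients. The downside is slightly longer recall for patients who enrol late.
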